6.1.2 ADMINISTRATION AND/OR DOSING

In each condition, the smartwatch will vibrate to alert PWA to a single naming trial (1-item condition) or naming trial set (9-item EMA condition). After the vibration alert, PWA will see a screen that says "Ready to name a picture?" (1-item condition) or "Ready to name some pictures?" (9-item EMA condition). If the participant taps YES, a picture will appear, and the device will begin recording audio. PWA will have up to five seconds to provide an oral response, after which a "Thanks!" screen will appear. The fivesecond response window was selected based on research showing that PWA correctly name pictures within 3.5 seconds, on average, with longer response latencies for incorrect responses. If a participant fails to respond to a vibration prompt or pushes the NO button to the "Ready?" screen, they will be reprompted five minutes later via one more vibration alert. During the three-week EMA protocol, each participant will attempt to name 108 unique objects derived from the 260-item Snodgrass and Vanderwart photoset. The subset of pictures presented to each participant will be based on their naming evaluation (during week 1, session 1). When possible, half of the pictures will be items the PWA named correctly during the evaluation, and the other half will be incorrectly named pictures. This approach will allow us to gauge naming variability over time of items PWA are able versus unable to name during traditional SLP assessment, providing an important window into anomia. To mitigate practice effects, the individual pictures (1-item condition) or picture sets (9-item EMA condition) will be presented randomly without replacement until all 108 pictures have been presented, and then the picture cycle will restart. In both conditions, 36 naming trials will be scheduled per day, resulting in a total of 756 scheduled trials for each participant across the experiment. In the 1-item EMA condition, single-naming trial prompts will appear at random intervals from 10am to 8pm. In the 9-item EMA condition, PWA will receive four prompts per day to complete a set of nine picture naming trials per prompt; one prompt will be scheduled in every 2.5-hour block between 10am and 8pm.

15 March 2022

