8.1 ENDPOINT AND OTHER NON-SAFETY ASSESSMENTS

Endpoint Assessments: Feasibility will be classified in three ways: (1) PWAs' adherence to the smartwatch μΕΜΑ or EMA protocol via compliance and completion, (2) PWAs' perceived burden of completing the EMA protocol, and (3) speech intelligibility of recorded naming attempts. Currently, PWAs' capacity for adhering to a smartwatch EMA protocol via button press responses or verbal responses is unknown. As such, compliance will be based on the number of YES button responses to the "Ready?" screen whereas completion will be based on naming attempts. Specifically, similar to [name] et al. (2016), compliance will be determined by the number of YES responses over scheduled trials, including trials missed due to the watch being off/uncharged. Completion will be calculated as trials with captured audio (reflecting attempted naming) over delivered trials, excluding trials missed to the watch being off/uncharged. Perceived burden will be measured via responses to the weekly surveys during weeks 2-4. Finally, speech intelligibility will be measured by a categorical rating of responses captured in each audio clip (i.e., completely intelligible, partially intelligible, or completely unintelligible).

Other Non-Safety Assessments: Before the EMA period, PWA will be administered the following testing battery. The Quick Aphasia Battery (QAB) will be used as our eligibility assessment and to measure overall aphasia severity. The Pattern Comparison Processing Speed Test and Flanker Inhibitory Control and Attention Test from the NIH Cognition Toolbox will be used to measure non-linguistic visual attention and executive functions, respectively. We will use brief, standardized picture description and story elicitation tasks from the AphasiaBank protocol to index anomia in discourse. Participants will complete an overt object naming test twice before EMA and once after EMA so that the research team can evaluate word retrieval via the standard SLP assessment format (i.e., single administration in a quiet 1:1 interaction). This picture naming probe will include normed real photos of the 260 items from the Snodgrass and Vanderwart stimuli set. Before EMA, PWA will also participate in an intake interview and complete a questionnaire about their comfort with technology, adapted for aphasia (simple language, short phrases).

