9.2 SAMPLE SIZE DETERMINATION

For the Aim #1 logistic mixed effects models, two groups of 10 PWA per group will achieve 80% power to detect an odds ratio of 1.20 in a design of 756 repeated measures with a AR(1) covariance structure and when the correlation between observations of the same subject is 0.600 and alpha is 0.05. If the proportion of completed trials for the EMA group is 0.500, a statistically significant result will occur if the μ EMA group proportion is 0.545 or greater. In [name] et al.4, the mean difference in proportions between the μ EMA and EMA conditions was >0.20 for compliance and completion, which is much higher than the needed 0.045 difference. This suggests we will have ample power to detect significant differences between the two conditions.

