9.4.2 ANALYSIS OF THE PRIMARY ENDPOINT(S)

We will code each trial in the EMA time series to index compliance, completion, and speech intelligibility. Every scheduled trial (n = 756 total trials) will be coded as 0 for a nonresponse/ NO button

Version 1.000

Protocol 15 March 2022

response or 1 for a YES button response, reflecting compliance. Every delivered trial with a naming attempt captured on audio (n trials will vary by person) will be coded as 0 for incomplete or 1 for complete, reflecting completion. For each of these measures, we will run a logistic mixed effects model with one of the feasibility measures (i.e., compliance, completion) as the dependent variable, condition (1-item vs. 9-item) as the independent variable, and random effects of participant and trial.

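### The 80% power in 9.2 assumes no lasting differences between participants, although condition is compared between 10 and 10 people; 0.545 is the design alternative, not the significance boundary

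*Combined protocol and SAP*

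**What the plan says.** Section 9.2 sizes the study for the logistic mixed models: two groups of 10 have "80% power to detect an odds ratio of 1.20 in a design of 756 repeated measures with a AR(1) covariance structure", within-subject correlation 0.600 and alpha 0.05. Taking 0.500 for the 9-item group, it adds that "a statistically significant result will occur if the" 1-item proportion reaches 0.545. It then cites a difference above 0.20 from an earlier study, "which is much higher than the needed 0.045 difference", and concludes: "This suggests we will have ample power to detect significant differences between the two conditions".

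The model in 9.4.2 has condition as the predictor and "random effects of participant and trial"; no AR(1) term is mentioned. For compliance, "Every scheduled trial (n = 756 total trials) will be coded as 0" or 1.

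Section 8.1 says "compliance will be based on the number of YES button responses to the" Ready screen. In the 9-item condition, 6.1.2 says "PWA will receive four prompts per day to complete a set of nine picture naming trials per prompt".

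Section 9.1 makes higher compliance and completion in the 1-item condition the primary hypothesis.

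**The concern.** Each person receives one condition, so the comparison is between 10 and 10 people. Its precision is governed by how much people differ from one another over the three weeks, and further trials from the same person do not remove that variation. An AR(1) structure with correlation 0.600 has no such component: the correlation is below 0.01 by lag 10 (0.6^10 = 0.006), well within one day's 36 trials.

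The plan itself expects lasting differences. Section 5.3 foresees that some participants will have more difficulty, 6.3 balances the conditions on aphasia severity, and 9.4.9 correlates the feasibility measures with stable personal factors.

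Section 9.2 is the only numerical support for testing the primary hypothesis with this sample. If it stands, a non-significant result could be read as no difference between delivery schedules, and a later study could be sized on 0.045.

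**Working it through.** **Inputs from 9.2:** 10 per arm, m = 756 trials each, AR(1) with lag-1 correlation 0.600, alpha 0.05, p1 = 0.500, odds ratio 1.20. Sidedness is not stated; two-sided reproduces the stated power. **Not in the documents:** any between-participant SD or ICC. Every ICC and SD below is an assumption.

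**1. Reproducing the 80%.**
- p2 = 1.2/2.2 = 0.5455, a difference of 0.0455.
- Design effect D = 1 + 2 Σ (1 − j/756) 0.6^j, j = 1 to 755, which is 3.990. Each person counts as 756/3.990 = 189.5 independent trials.
- SE = √[(0.2500 + 0.2479) × (3.990/756)/10] = 0.01621.
- Power = Φ(0.0455/0.01621 − 1.96) = 80.1%.
- The implied SD of participants' observed three-week proportions is √(0.25 × 3.990/756) = 0.036.

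**2. The boundary on the same inputs.** 0.500 + 1.96 × 0.01621 = 0.532. The value 0.545 is p2, the alternative.

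**3. Adding lasting participant differences.** The variance of one participant's proportion becomes p(1 − p)[ICC + (1 − ICC) × 3.990/756]. The SD of true proportions at 0.500 is √(0.25 × ICC). For ICC = 0.01 the bracket is 0.01 + 0.99 × 0.005278 = 0.01523, so SE = √(0.4979 × 0.01523/10) = 0.0275 and power = Φ(0.0455/0.0275 − 1.96) = 38%.

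| Assumed ICC | SD of true proportions | Power, normal | Power, t on 18 df | Boundary (normal) |
|---|---|---|---|---|
| 0 | 0 | 80% | 76% | 0.532 |
| 0.001 | 0.016 | 73% | 68% | 0.535 |
| 0.005 | 0.035 | 52% | 48% | 0.544 |
| 0.01 | 0.050 | 38% | 35% | 0.554 |
| 0.02 | 0.071 | 25% | 23% | 0.569 |
| 0.05 | 0.112 | 14% | 13% | 0.603 |

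The boundary passes 0.545 at an ICC of about 0.0056. A simulation of binary AR(1) series with beta-distributed participant means (4,000 runs) gave 38.8% (normal) and 34.4% (t) at ICC 0.01.

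**4. Compliance.** As 6.1.2 reads, one YES opens a set of nine, so a 9-item participant gives 4 × 21 = 84 answers. With independent answers and no lasting differences, SE = √[(0.25/84 + 0.2479/756)/10] = 0.0182. Power for odds ratio 1.20 is then 71% (normal) or 66% (t). Simulated with logit-normal participants and a t-test (40,000 runs), it is 52% and 32% at logit SDs of 0.1 and 0.2. For 0.50 v 0.70 on this basis, power is about 100% at logit SD 0.3, 92% at 0.5 and 42% at 1.0.

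**5. The 0.20 difference.** In a participant-level t-test, SE = SD × √0.2, the noncentrality for 80% power is 2.963, and the critical value is 2.101. SD here is that of participants' observed proportions.

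| Assumed SD | Power for 0.20 | Detectable at 80% (2.963 × SE) | 95% CI half-width (2.101 × SE) |
|---|---|---|---|
| 0.10 | 99% | 0.13 | 0.09 |
| 0.15 | 80% | 0.20 | 0.14 |
| 0.20 | 56% | 0.27 | 0.19 |
| 0.25 | 39% | 0.33 | 0.23 |

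**The case against.** The best defence is that the conclusion in 9.2 rests on an expected difference above 0.20, not on an odds ratio of 1.20. With AR(1) kept, power for 0.50 v 0.70 is about 100% at ICC 0.01, 98% at 0.05 and 82% at 0.10 (normal approximation). That stands: the ICC that reduces power for 1.20 to 38% leaves power for 0.20 intact. It still depends on an unstated SD, and power falls to 54% at ICC 0.20. The cited difference may also come from neurotypical people, as the pilot results in 2.2 do; the source is not visible, so little weight is put on this.

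Second, the 38% combines AR(1) with a participant effect, whereas 9.4.2 names no AR(1) term. Dropping AR(1) gives 91% at ICC 0.0025 but 48% at 0.01. Solving ICC + (1 − ICC)/756 = 0.005278 shows that 80% then needs an ICC of about 0.004 or less, an SD of true proportions of about 0.03. The point survives.

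Third, 9.2 says if, not only if, and an observed 0.545 does exceed 0.532. That is so on its own inputs, but calling 0.045 the needed difference still presents the alternative as the threshold.

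Fourth, the 84-answer point does not touch completion, which 8.1 bases on captured audio. Agreed; it applies to compliance only.

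Finally, this is a pilot, and 6.1.1 describes the comparison as preliminary. That limits the consequences, but it argues for estimation language rather than a definite power claim.

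**Conclusion.** The concern holds. The arithmetic in 9.2 is right for the model it assumes, but that model leaves out the variance that governs a 10 v 10 comparison and that 9.4.2 includes. The 80% therefore applies only if lasting participant differences are close to nil; an SD of five percentage points in true rates more than halves it. The reading of 0.545 and 0.045 as thresholds is wrong without any added assumption. The figure of 0.532 should not replace it, because it too assumes no participant variance. Ample power for 0.20 is plausible if the SD of participants' proportions is about 0.15 or less, and unsupported above that. The exact power losses depend on assumed ICCs and SDs, and the 84-answer count on reading 6.1.2 as one Ready answer per set. The feasibility objective itself is not affected.

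**What to change.** In 9.2, delete the statement of 80% power for an odds ratio of 1.20, the sentence on 0.545, the reference to 0.045 as the needed difference, and the claim of ample power. Suggested replacement:

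> The condition effect is estimated from 10 v 10 participants. As a participant-level t-test approximation to the planned mixed model (two-sided alpha 0.05), if the SD of participants' compliance or completion proportions is 0.10, 0.15, 0.20 or 0.25, the difference detectable with 80% power is about 0.13, 0.20, 0.27 or 0.33, and the 95% CI half-width is about 0.09, 0.14, 0.19 or 0.23. These SDs are assumptions; the comparison is preliminary. In the 9-item arm, compliance rests on 84 YES/NO answers per person.

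In the report, give each condition's mean and the difference with participant-based 95% CIs, and the observed between-participant SD, which a later study will need.

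The cost is one reworded paragraph, a few added summaries and a less favourable stated power. Enrolment and the 9.4.2 model stay as they are.

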2.2 BACKGROUND

Impaired word retrieval—also known as anomia—is one of the most debilitating symptoms stroke survivors with aphasia, a communication disorder characterized by impaired language, face in their daily lives. Like "tip-of- the-tongue" states experienced by neurotypical individuals, anomic moments in people with aphasia (PWA) occur when an individual knows what they want to say but cannot retrieve the word. Unlike "tip-of-the-tongue," anomia in PWA pervades communication exchanges and is characterized by inconsistent ability to retrieve a given word across attempts. The severity and unpredictability of anomia lead many PWA to disengage from conversation and social situations, which can severely impact their participation and quality of life. In daily life, anomia can be further compounded by real-world communication contexts such as attempting to communicate in distracting settings (e.g., with background noise and/or other people in the vicinity) or when completing other tasks. In clinical practice, speech-language pathologists (SLPs) typically assess anomia by administering a standardized test once to a patient in a quiet room. This approach captures neither the variability typical of post-stroke anomia nor the realities of real-world communication. In contrast, ecological momentary assessment (EMA) is a method often used in health research to measure physical, mental, or cognitive states in a person's daily life over several days, weeks or even months. Traditional EMA involves a device prompting a participant to answer a set of questions a few times a day, whereas micro-interactionbased EMA (µEMA) uses single-question, "at-a-glance" prompts that are interspersed over time rather than grouped into sets. Our pilot studies demonstrate that µEMA has higher response rates and lower perceived burden than traditional EMA in neurotypical individuals despite its higher interruption rate. Thus, we propose that EMA—particularly µEMA—is a viable approach to capture real-world anomia in PWAs' daily lives. Yet, despite the increasing use of technology-based assessments and therapy platforms for PWA, neither EMA nor µEMA methods have been utilized in aphasia.

Version 1.000

Protocol 15 March 2022

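### Section 9.2's claim of ample power compares an effect that cannot come from people with aphasia with a 0.045 threshold that holds only if participants hardly differ from one another

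*Combined protocol and SAP*

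**What the plan says.** Section 9.2 states that "two groups of 10 PWA per group will achieve 80% power to detect an odds ratio of 1.20", for "a design of 756 repeated measures with a AR(1) covariance structure", where "the correlation between observations of the same subject is 0.600 and alpha is 0.05". The reference case is given as "If the proportion of completed trials for the EMA group is 0.500", against 0.545 in the micro-EMA group. The section then cites a study in which the two delivery schedules differed by more than 0.20 on completion and on compliance alike, "which is much higher than the needed 0.045 difference. This suggests we will have ample power to detect significant differences between the two conditions".

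Elsewhere the plan describes what was known beforehand. Section 2.2 says its pilot work found that micro-EMA "has higher response rates and lower perceived burden than traditional EMA in neurotypical individuals despite its higher interruption rate". It adds that neither EMA nor micro-EMA "methods have been utilized in aphasia". The synopsis (1.1) also says EMA is untested in this population, and section 8.1 says participants' "capacity for adhering to a smartwatch EMA protocol via button press responses or verbal responses is unknown". Section 2.1 is softer and speaks of little EMA research in stroke survivors with aphasia.

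Section 9.4.2 specifies logistic mixed models for compliance and completion, with condition as the fixed effect and random effects of participant and trial. It names no AR(1) term.

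**The concern.** The step from 80% power for a small effect to ample power rests on one comparison: a large expected difference against a small detectable one. If the expected difference was not observed in people with aphasia, its size here is an assumption. If the detectable difference depends on participants being almost identical in their response rates, the margin between the two is not established either.

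Section 9.1 makes superiority of the 1-item schedule the primary hypothesis. If the comparison turns out non-significant in a trial described as amply powered, a reader could take that as evidence that the two schedules do equally well in aphasia. Ten participants per arm may be unable to support that reading.

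**Working it through.** **Inputs from section 9.2.** 10 participants per arm, 756 trials each, AR(1) with rho = 0.6, alpha 0.05 (two-sided reproduces the figure), odds ratio 1.20, reference proportion 0.500. The odds ratio gives 1.2/2.2 = 0.5455 in the other arm, a difference of 0.045.

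**Step 1: the plan's own figure.** The AR(1) design effect is 1 + 2·Σ(1 − k/756)·0.6^k for k = 1 to 755, which is 3.99. The effective number of trials per arm is 10 × 756 / 3.99 ≈ 1,895. A two-sided comparison of 0.500 with 0.5455 at that size has power 0.800, so the stated 80% reproduces. It does not use the 0.20. Under the same inputs, power is 87% at a difference of 0.05 and above 99.9% at 0.10 and 0.20.

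**Step 2: what AR(1) implies about people.** The SD of one participant's observed proportion around the arm mean is √(0.25 × 3.99 / 756) = 0.036. The correlation between two trials ten apart is 0.6^10 = 0.006, and between trials a day apart (36 trials) it is effectively zero. Under this structure, how often someone responds on one day says almost nothing about the next day, and lasting differences between people are assumed away. The plan expects such differences: 9.4.2 fits a participant random effect, and 9.4.9 relates each person's compliance and completion to age, aphasia severity, cognition and comfort with technology.

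**Step 3: power when people differ.** The plan gives no between-participant SD, so the values below are assumptions. The approximation is a two-sample t-test on participant proportions: df = 18, critical t = 2.101, noncentrality = d / (SD × √(2/10)), both tails counted. For example, d = 0.20 and SD = 0.15 give 0.20 / (0.15 × 0.447) = 2.98 and power 80.5%.

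| True difference | SD 0.10 | SD 0.15 | SD 0.20 | SD 0.25 |
|---|---|---|---|---|
| 0.05 | 18.5% | 10.9% | 8.3% | 7.1% |
| 0.10 | 56.2% | 29.2% | 18.5% | 13.5% |
| 0.15 | 88.7% | 56.2% | 35.5% | 24.6% |
| 0.20 | 98.8% | 80.5% | 56.2% | 39.5% |

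**Step 4: cross-check by another route.** A participant random intercept implies roughly exchangeable correlation, with design effect 1 + 755 × ICC. At assumed ICCs of 0.05, 0.10 and 0.20 the design effects are 38.75, 76.5 and 152. By the Step 2 formula these correspond to participant-level SDs of 0.11, 0.16 and 0.22. Power at 0.20 (normal approximation) is then 98%, 82% and 53%, in line with the table. If the stated 0.600 were itself exchangeable, the design effect would be 1 + 755 × 0.6 = 454, the effective trials per arm 7,560 / 454 = 16.7, and power at 0.20 about 21%.

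**Step 5: where the 0.20 can come from.** Sections 1.1 and 2.2 say the methods had not been tested or used in aphasia, and 8.1 calls adherence unknown. On that account the cited study cannot supply an aphasia estimate. Section 9.2 does not say so and gives no reason for carrying the figure over.

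**The case against.** The strongest reply is that the borrowed effect does little harm on the plan's own terms. The 80% does not depend on it, and under AR(1) three quarters of it could vanish and power would still be 87% at 0.05. The wording is hedged, the study is a feasibility pilot, and using the nearest available data is normal practice. This stands as far as it goes: if AR(1) with rho 0.6 were right, the source of the 0.20 would hardly matter. But the fourfold margin is itself a product of AR(1), so it cannot be used to defend the conclusion against Step 3.

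Some stronger readings are tempting, and the documents do not support them:

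- *The 0.20 was observed in neurotypical people answering at-a-glance questions.* Section 2.2 mentions neurotypical pilot work and defines micro-EMA in those terms, but nothing identifies that work as the study cited in 9.2. Only the negative holds: it was not aphasia data.
- *The task mismatch undermines both primary endpoints.* Compliance needs only a YES tap (8.1). Speech matters only for completion, and the cited study's task is not described.
- *Thirty-six prompts a day may cost this group more than four.* Both arms are scheduled for 36 naming trials a day (6.1.1). A reversal of the effect would be speculation.
- *The full 0.20 must carry over for the trial to have adequate power.* That depends on the assumed SD. At 0.10, a difference of 0.15 has 89% power.
- *A null result will be read as equivalence.* No section says so. It is a risk to guard against.

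**Conclusion.** The concern holds for the ample-power conclusion. The 80% for an odds ratio of 1.20 is arithmetically correct under its stated inputs. What fails is the inference from it, because the expected effect is unknown in this population and the detectable difference of 0.045 requires a between-participant SD of about 0.036, which does not fit the planned random effect.

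The size depends on an SD that the plan does not give. Over 0.10 to 0.25, power at the full borrowed difference runs from 99% to 40%, and at half of it from 56% to 13.5%. These figures approximate the planned mixed model by a t-test on participant proportions. They do not prove the trial underpowered. They show that adequate power depends on two unknowns, which 9.2 treats as settled. The population point alone would have little numerical consequence; it matters because the AR(1) margin cannot be relied on to absorb it.

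**What to change.** In section 9.2:

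1. Delete the sentence that concludes power is ample.
2. State that the difference above 0.20 is an assumption from outside aphasia and that no aphasia estimate is available. Reconcile the wording of 2.1 with that of 1.1 and 2.2.
3. Give power for 10 versus 10 participants at true differences of 0.05, 0.10, 0.15 and 0.20 over a stated range of between-participant SD or ICC. Obtain it by simulating the 9.4.2 mixed model, or use a participant-level approximation such as the table above and label it as one.

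In section 9.4.2, commit to reporting the condition effect with its 95% confidence interval, and say that a non-significant result will not be read as showing no difference between schedules.

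The cost is some rewording, a short table and, if chosen, a modest simulation. Enrolment and procedures are unchanged. The downside is a less favourable power statement.
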